There are no direct benefits to the subject for participating in the brain imaging portion of the research. Broader scientific benefit, as discussed elsewhere in this application, is potentially large. Other benefit to participants will be limited to their education as a result of self-report assessment and neuropsychological recording.

For the IASIS treatment portion of the research, the Veterans may experience reduced post-concussive symptoms (e.g., post-traumatic headache, photophobia, memory problems, and sleep disturbance symptoms), and improved cognitive functions. The procedures of the study involve minimum risk, as discussed above, and the risks encountered can be easily managed. Thus, the risk/benefit ratio favors the benefit.

For Veterans who complete the IASIS treatment, participants may experience reduced post-concussive symptoms, as listed in the paragraph above.

Section 18 - Risk/Benefit Analysis

18) Discuss why the risks to subjects are reasonable in relation to the anticipated benefits to subjects and in relation to the importance of the knowledge that may reasonably be expected to result.

The procedures of the study involve minimum risk, as discussed in Section 17: Potential Benefits, and the risks encountered can be easily managed. Thus, the risk/benefit ratio favors the benefit.

Section 20 - Compensation for Participation

20) Provide all details and justifications of the compensation plan. See ? for detailed requirements.

As of 09/30/2022, funding for this study ended and participant study visits/sessions stopped.

During the data collection period, each participant received between \$225 - \$900 total for participation in MEG's (\$75 each), MRI (\$75 each), neuropsychological exam and mental health assessment (\$75 each session), and IASIS or Sham sessions (\$300).

If the Veteran participated in Nexalin treatments, he or she will receive up to \$500 for total participation. Specifically, they received \$75 for every full hour of MEG and \$25 per Nexalin session (amounting to \$250-\$500 for 10 up to 20 Nexalin sessions).

Controls underwent 1 NP/MHA visit, 1 MEG, and 1 MRI. A subset of controls will receive a second MEG for retest comparison.

All participants were compensated \$40 per round trip visit to the UCSD RIL/UCSD CfMRI to cover transportation costs of gas, bus fare, ride sharing expenses, etc.

Participants in the TBI group with IASIS neurofeedback received 1 NP/MHA visit, 1 MEG, and 1 MRI all at baseline/pre-IASIS, 12 IASIS sessions, 3 MEG's throughout the IASIS sessions, 1 post-IASIS MEG, and 1 post-IASIS NP/MHA. A subset of the TBI group with IASIS neurofeedback received 1 additional follow-up MEG one month post-IASIS.

Participants in the TBI group with SHAM IASIS completed 1 NP/MHA visit, 1 MEG, and 1 MRI all at baseline/pre-Sham IASIS, 12 Sham IASIS sessions, 3 MEG's spread throughout the Sham

IASIS sessions, 1 post-Sham IASIS MEG, and 1 post-Sham IASIS NP/MHA.

Participants in the TBI group with Nexalin TES received 1 MEG at baseline/pre-Nexalin, 10-20 Nexalin sessions, and 1 post-Nexalin MEG.

Participants in the TBI group with Nexalin-sham completed 1 MEG at baseline/pre-Nexalin, 10-20 Nexalin sessions (sham sessions will be administered), and 1 post-Nexalin MEG.

If a participant discovered that they were in an IASIS Sham, or Nexalin Sham condition, they may have chosen to undergo the true treatment. If they did so, they were compensated in accordance with the respective values listed above for their treatment.

Subjects were offered a picture of their brain MRI containing 1 sagittal slice, 1 axial slice, and 1 coronal slice of their T-1 scan. Subjects were reminded that this picture is not completed for clinical purposes. Also, this picture would not contain any subject information nor any personal information.

Section 21 - Responsibilities and Qualifications

Here are the identified study staff members

[name]

[name], [name], [name], [name], [name], [name] [name], [name], [name], [name], [name], [name], [name], [name]

21) For each staff member listed above, describe their role and qualifications. Also indicate which of the study staff are authorized to obtain consent, when applicable to the study.

[name]*, Ph.D., (PI) has privileges at the VA and UCSD Medical Centers and will be in charge of the MEG and MRI.

[name]*, M.D.,(Co-I) is a psychiatrist at the VA. She will assist in referring participants to this study.

[name], M.D., (Co-I) has privileges at the VA and UCSD Medical Center, and will be analyzing the MRI scans.

[name] (Co-I) is a licensed neuropsychologist for UCSD. She will oversee the neuropsychological testing session for this pilot study.

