3 in order to confirm the test-retest-reliability of the normative database. In contrast, at Visit 3 the mTBI participants in IASIS and sham groups will undergo a pre-session MEG, the first IASIS /Sham treatment session (S1), and a post-session MEG exam. The pre-session MEG in Visit 3 can be used as a re-test exam with respect to the Visit 2 baseline MEG for analyzing test-retest-reliability in the mTBI groups. In addition, the same pre-session MEG exam in Visit 3 will be compared with Visit 3 post-session MEG to assess possible potentiation of slow-waves due to the IASIS session (or lack of potentiation in the sham session). Next, the mTBI participants continue their IASIS/Sham treatment sessions (S2-S6) in visits 4-8. During the mid-treatment Visit 9, another pair of pre- and post-session MEG exams and NP will be performed. The mTBI participants will continue treatment sessions (S8-S11) in Visits 10-13. During the final treatment Visit 14, the third pair of pre- and post-session MEG exams will be performed. One week after the participants finish their final IASIS/Sham treatment session (S12), a one-week follow-up MEG and NP exams will be conducted during Visit 15. Finally, a subset of IASIS group (N=25) will be tested one month after the final treatment for a one-month follow-up MEG. To reduce drop-out rate, participants initially in the mTBI-sham group will also be offered the real IASIS treatment, but no MEG or behavioral data will be collected for that treatment. **Figure 10 - See attached document.** If, after IASIS treatment is complete and participants in the mTBI group may have remaining PCS, additional Nexalin treatment will be offered.

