D.1.2. Exclusion criteria for study participations include: 1) history of other neurological, developmental, or psychiatric disorders (based on the DSM-5 (MINI-7) [86] structured interview), e.g., brain tumor, stroke, epilepsy, Alzheimer's disease, schizophrenia, bipolar disorder, ADHD, or other chronic neurovascular diseases such as hypertension and diabetes; 2) substance or alcohol use disorders according to DSM-5 [87] criteria within the six months prior to the study; 3) history of metabolic or other diseases known to affect the central nervous system (see [88] for similar criteria); 4) Metal objects (e.g., shrapnel or metal fragments) that fail MRI screening, or extensive metal dental hardware (e.g., braces and large metal dentures; fillings are acceptable) or other metal objects in the head, neck, or face areas that cause non-removable artifacts in the MEG data; 5)

Potential subjects will be administered the Beck Depression Inventory (BDI-II) to evaluate level of depressive symptoms, and suicidal ideation; any participant who reports a "2" or "3" on the BDI-II: item 9 (suicidal thoughts or wishes) will also be excluded. However, depression following mTBI or traumatic event of PTSD is common [89]; therefore, in two mTBI groups, we will include and match patients with depression symptoms reported after their injury/event, and will co-vary BDI-II score in data analyses.

D.1.3. Inclusion for the mTBI groups: All symptomatic mTBI patients will be evaluated in a clinical interview to document the nature of the injuries and ongoing PCS. The diagnosis of mTBI patients is based on standard VA/DOD diagnostic criteria. Inclusion in the mTBI patient group requires a TBI that meets the following criteria: 1) a loss of consciousness (LOC) < 30 minutes or transient confusion, disorientation, or impaired consciousness immediately after the trauma; 2) post-traumatic amnesia (PTA) < 24 hours; 3) an initial Glasgow Coma Scale (GCS) [90] between 13-15 (if available). Since the GCS assessment is often not available in theater, Veterans with missing GCS, but who meet other inclusion criteria will also be recruited. Each patient must have at least 3 items of persistent PCS (see below) at the beginning of the study.

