
neuropsychological / symptom variables when using FDR correction. **Time Table of Tasks: See attachment.**

D.9 Combining data from pilot study, H150047

In order to complete data analysis with a larger sample size, we plan to combine data from pilot study H150047 for future analysis and publications. The data that will be combined will only be de-identified data from neuropsychological testing, IASIS treatments, MEG sessions, and MRI scans, using study numbers. Participants from this pilot study will not be re-consented and no waivers or consent or authorization will be needed in order to use the previously collected de-identified data.

Phase Orange COVID-19 Adoptions:

In compliance with VASDHS Policy, in-person interaction with research subjects during the COVID-19 pandemic, Phase Orange, will be limited to activities only viable if conducted in-person. Data collected in-person will be limited to consenting, MEG and MRI scan sessions, as well as IASIS, Nexalin, and/or TUNS treatments. Other aspects of participation, to include questionnaires, clinical interviews, and neuropsychological tests not requiring in-person interaction may be conducted remotely via phone. If appropriate or preferred by volunteers, forms, questionnaires, clinical interviews, and neuropsychological testing can be conducted in a private room, or outside (e.g., car, etc.) when performed in conjunction with an in-person study session, or in a testing room with appropriate social distancing, personal protective equipment (PPE), and sneeze guards. These adaptions will not change the data collected by this study (aside from the temporary removal of the TOMM, DEKFS Trail-making, WAIS-IV Symbol Search, WASI Matrix, DKEFS Color Word Interference, and WAIS-IV Digit Symbol Coding the neuropsychological testing battery due to concerns over shared surfaces and materials if neuropsychological testing was collected over the phone), and will allow the study to operate in full compliance of Phase Orange guidelines.

Section 9.4 Devices

9.4) For each research device, state the status of the device, the PI's determination as to whether the device is a significant or non-significant risk device, and provide justification for this determination. A copy of determinations from the FDA should be attached. - Also, for investigational devices describe how and by whom the device will be received, stored, secured and dispensed.

Device Classification Name: Device, Biofeedback
510(K) Number: K971708

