2) Subjects' head and neck will be padded and legs supported to make him/her as comfortable as possible during both MEG and MRI exams. Two-way intercom is available for both MEG and MRI. Unlike the MRI, there is no window on the MEG shielded room, so a video camera will be used inside the shielded room to monitor the subjects. No recordings of images during video camera monitoring while in the MEG shielded room will be performed or retained. For the MRI scans, the subjects will be provided with sound-attenuating ear-plugs before the imaging session and instructed on their use.

3) Subjects will be screened for claustrophobia. Those with claustrophobia will be excluded. Subjects may communicate with the operator of the scanner through the intercom at any time. The subject may request at any time that the experiment be terminated.

4) Members of the research team will be available to discuss any upsetting or discomforting emotions. If there appears to be a high level of upsetting or discomforting emotions during the study, or a high level of symptoms, as determined during CAPS interview, then a detailed assessment by the study

licensed clinician as well as the study investigator ([name]) may occur, where various options (such as referral to the subjects clinician or the VASDHS same day clinic) will be provided.

Additionally, should a participant report a "2" or "3" on the Beck Depression Inventory-II: item 9, regarding suicidal ideation, study procedures will include a brief assessment for safety by the study licensed clinician (psychologist) with consultation with [name]. Unless there is clear and imminent risk to the life of the Veteran, full confidentiality will be maintained. If subject safety is a concern, the subject will be referred to further treatment, and will be removed from the study.

5) To protect the privacy of study participants, an identifier card with a unique subject number will be created for each subject. All identifiable data will be recorded only on this card and the card will be destroyed upon completion of data analysis for the study. Subjects will be identified only by the unique subject number on all other data collection forms and in study databases.

Throughout the term of the study, identifier cards will be kept in a locked file cabinet in a separate room from the study data. MRI data files are also identified by the date of the scan.

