Safety of participants is ensured by procedures described in detail above. These procedures are supervised by a team of physicians, psychologists, physicists, and biologists with extensive experience in physical and mental health treatment, imaging, and psychophysiological testing. Briefly, participants are evaluated for co-morbid major psychiatric or substance use disorders and referred for care as indicated at baseline if they are not already members of a VASDHS clinic; those who enroll are assessed for deterioration of their clinical condition, distress, and suicidality, by the study psychologist and study physician, a psychiatrist during study participation and those with psychiatric disorder or depressed mood or suicidality not already under a clinician's care will be referred as indicated.

With our previous and ongoing studies we have developed a standardized procedure for reporting findings of clinical significance. The appropriate clinician will be contacted in a referral process for additional imaging and clinical care. We work in close contact with the clinicians in the TBI clinic at the VA San Diego as well as multiple other VA network clinicians. Additionally, Co-Is [name] on the study are directly involved in clinical care and can make any necessary proper referrals.

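### A safety removal after assignment takes the participant out of the study, not only out of treatment, and leaves no planned Visit 15, so missing H4/H5 data can depend on outcome

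*Combined protocol and SAP*

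**What the plan says.** **Removal.** Section 15 (Risk Management), item 4, covers a participant whose answer to one BDI-II question scores 2 or 3. The passage reads: "Beck Depression Inventory-II: item 9, regarding suicidal ideation, study procedures will include a brief assessment for safety by the study licensed clinician". The paragraph ends: "If subject safety is a concern, the subject will be referred to further treatment, and will be removed from the study".

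**Eligibility.** D.1.2, repeated in Section 10, uses the same item: "Potential subjects will be administered the Beck Depression Inventory (BDI-II) to evaluate level of depressive symptoms, and suicidal ideation". Anyone answering 2 or 3 on "item 9 (suicidal thoughts or wishes) will also be excluded".

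**Monitoring.** Later in Section 15, "those who enroll are assessed for deterioration of their clinical condition, distress, and suicidality". Participants with psychiatric disorder, depressed mood or "suicidality not already under a clinician's care will be referred as indicated". Removal is not mentioned there.

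**Schedule and analysis.** D.1.1 times the endpoint visit from the last session: "One week after the participants finish their final IASIS/Sham treatment session (S12), a one-week follow-up MEG and NP exams will be conducted", at Visit 15. D.1.6 collects the past-week CAPS-5 before treatment and at Visit 15, and the PCL-5 at Visits 1 and 15. D.5 collects post-concussive symptoms (RPQ, NSI) at every visit, but names Visit 15 against baseline as the main comparison and models two time points, group and their interaction.

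**The concern.** Stopping treatment and leaving the study are different events. The first need not cost any outcome data; the second does. Section 15 observes the difference elsewhere: in item 10, persistent headache or nausea on Nexalin ends treatment only. For item 9 with a safety concern, the consequence is exit from the study.

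The reason for exit is related to what is being measured. H5 concerns PTSD symptoms, and the NSI used for H4 includes emotional symptoms. If removals after assignment fall unevenly between arms, and those removed were doing worse, the remaining participants flatter the arm that lost more of them. The trial would also have no planned record of how these events resolved, although the DSMB (Section 9.9) reviews adverse events every six months.

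**Working it through.** **1. What happens to an assigned participant removed mid-course**

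- Visit 15 is one week after session 12 (D.1.1). Without a session 12 there is no Visit 15 date.
- CAPS-5 (past week) and PCL-5 have no value between baseline and Visit 15 (D.1.6), so H5 has no post-baseline value at all.
- RPQ and NSI exist up to removal (D.5), but the H4 model has only two time levels and does not use them. D.4.3 describes this type of ANOVA as equivalent to a linear mixed model. Fitted that way, the participant's baseline value stays in, but still with no information on change.
- The visible text has no early-termination visit, post-removal follow-up, definition of the analysis population or missing-data rule.

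**2. The three item 9 provisions side by side**

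| Place | Applies to | Consequence |
|---|---|---|
| D.1.2 and Section 10 | potential subjects scoring 2 or 3 | exclusion, unconditional |
| Section 15, item 4 | a participant scoring 2 or 3 | safety assessment; removal if safety is a concern |
| Section 15, later summary | enrolled participants, suicidality | referral if not already in care |

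The text does not say which applies before assignment and which after.

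**3. The plan's own power figures**

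Inputs from D.8: 50 per arm (N = 100), two-tailed α = 0.01, f = 0.38 for RPQ and f = 0.32 for PCL; stated power > 0.95 and > 0.85. Assumption: correlation ρ = 0.5 between the m = 2 measurements (none is given). With the between-group form of repeated-measures ANOVA, df 1 and N − 2:

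λ = f² × N × m / (1 + (m − 1)ρ)

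- RPQ: 0.1444 × 100 × 2/1.5 = 19.25; power 0.959.
- PCL: 0.1024 × 100 × 2/1.5 = 13.65; power 0.855.

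These agree with the stated values and require all 100 participants to have data. (At ρ = 0.5 the time-by-group interaction would give above 0.999 for both, so the stated figures match the between-group form. It is used here only to gauge loss of precision.) With 98 participants the powers are 0.955 and 0.846; with 95, 0.948 and 0.832. A few removals cost little precision.

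**4. Bias**

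Suppose k of 50 in an arm are removed and their change would have been g SD worse than that of the rest of the arm. The all-assigned mean is [(50 − k)M + k(M + g)]/50 = M + kg/50, where M is the mean of those remaining. The remaining participants therefore look better by kg/50.

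- k = 1: 1 × 1/50 = 0.02 SD at g = 1; 1 × 2/50 = 0.04 SD at g = 2.
- Three removed in one arm and one in the other, g = 2: 0.12 − 0.04 = 0.08 SD. Reading f = 0.32 as d = 2f = 0.64, that is 0.08/0.64 = 12.5% of the planned PCL effect. At g = 1 it is half that.

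Type I error if there is no true effect and removals occur in one arm only, with unit SD and SE = √(1/(50 − k) + 1/50), at nominal two-sided 0.01:

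| k | g | Bias (SD) | Type I error |
|---|---|---|---|
| 1 | 1 | 0.02 | 0.0104 |
| 2 | 2 | 0.08 | 0.016 |
| 5 | 2 | 0.20 | 0.055 |

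The values of k and g are assumptions; the documents give neither.

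**The case against.** The strongest reply is that the rule may seldom reach an assigned participant. The BDI-II is given to potential subjects, and no visible passage schedules it after baseline. Consent precedes the baseline assessments (D.1.1, Section 11), so a consented person can fail item 9 at baseline and be removed with no arm and no endpoint to lose. This stands as a limit on size. It does not close the gap, because Section 15 monitors suicidality in those who enroll and does not confine item 4 to screening.

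Four stronger readings are tempting, and the documents do not support them:

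- *Everyone who deteriorates is removed.* The removal sentence closes the item 9 paragraph. High distress or high symptoms lead to assessment and options such as referral (Section 15, item 4), so most participants who worsen would stay and be measured.
- *Their data are never collected.* RPQ and NSI at each visit, the Visit 9 MEG and neuropsychological tests, and adverse events before removal are all planned. What lacks a plan is Visit 15 and the course after removal. There the text is silent; it does not forbid follow-up. The visit table and Figure 10 are also not visible.
- *The three provisions flatly contradict each other.* The later text in Section 15 introduces itself as a brief summary of the procedures above it, so omitting removal need not mean a different rule. What remains is an ambiguity about which consequence applies at which stage.
- *The effect estimate is biased by 12.5%.* That figure rests on an assumed split of removals and an assumed gap.

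It is also true that new assessments can no longer be added: enrolment has closed (Section 11.1) and visits stopped by 09/30/2022 (Section 20). That changes the remedy, not the point.

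**Conclusion.** The point holds in limited form. If a removal under Section 15, item 4 happens after assignment, the participant has no planned Visit 15, no stated adverse-event follow-up and no contribution to the two-time-point comparison of change. Missingness in H4 and H5 can then depend on outcome, and no analysis rule addresses it.

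The size cannot be determined, because the number, timing and arm of removals are not given. The illustration runs from negligible (one removal at 1 SD: type I error 0.0104 against 0.01) to material (five in one arm at 2 SD: 0.055). It assumes 50 per arm, unit SD, no true effect and one-sided loss. Bias is the main issue; the loss of precision from a few removals is small. The documents do not show that any such removal occurred.

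**What to change.** **Protocol wording.**

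- Reconcile D.1.2/Section 10, Section 15 item 4 and the later Section 15 summary, stating what applies at screening and what applies after assignment. The clinical rule at each stage is for the sponsor's clinicians.
- Separately, distinguish stopping study treatment from withdrawing from the study.
- Unless consent is withdrawn or the clinician advises against it, keep adverse-event follow-up and collect RPQ, NSI, PCL-5 and CAPS-5 at the scheduled Visit 15 date. Count that date from Visit 3: a six-week course plus one week, so about seven weeks later.
- The COVID-19 adaptations in Section 9 already state that "questionnaires, clinical interviews, and neuropsychological tests not requiring in-person interaction may be conducted remotely via phone"; this would need to become a standing provision.

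**Existing cohort, before analysis.**

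- Analyse every assigned participant in the assigned arm.
- For H4, replace the two-time-point ANOVA with a linear mixed model using RPQ and NSI from all visits, so that scores before removal count.
- Report removals by arm, reason and last visit, including those for failing the TOMM (D.1.9).
- Add a sensitivity analysis assuming worse outcomes for those removed. The mixed model relies on the observed scores explaining the missingness, and for H5 there are no interim CAPS-5 or PCL-5 values to help.

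**Cost.** Some wording, some analysis time and, in a future protocol, one assessment per early stopper. Values collected after treatment stops may partly reflect outside care and should be reported as such.
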